### 3.4.1 *Primary Efficacy Endpoints*

#### Primary Analysis

The primary efficacy endpoint analysis will include the following parameters: UPCR (Morning void), UPCR (24 hour Urine), and eGFR. This will be summarized by treatment group over time using descriptive statistics. Both change from baseline to Week 12, and percent change from baseline to Week 12 will be included in the summary.

Change and percent change from baseline in renal function will be based on eGFR (calculated using the CKD-EPI Cystatin C equation, the CKD-EPI Creatinine equation, the CKD-EPI Other Efficacy Endpoints

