## 2 STUDY OVERVIEW

### 2.1 Study Objectives

#### 2.1.1 *Primary Objective*

The Primary Efficacy Objective is to evaluate the effect of CCX140-B on proteinuria in subjects with primary FSGS with nephrotic syndrome, assessed as a median reduction from baseline of urine protein to creatinine ratio (UPCR) of at least 20 % i.e.  $\geq 20\%$  by Week 12.

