Lymphocyte Subset 		X	X	X		X		X		X		X			X			X		

Visit D(ays) +/- 3 days & W(eeks) +/- 1 week	Scr	D 1	D 15	D 29	D 43	D 57	D 71	D 85 or w k 12	Wk 16	Wk 20	Wk 24	Wk 28	Wk 32	Wk 36	Wk 40	Wk 44	Wk 48	Wk 52 or Early Term Visit (for any reason)	7 and 14 days post final dose	Follow up Visit (4 wks post final dose)
PK AUC plasma sample 		X		X		X														
PK C min sample			X		X															
PK concentration sample																	X	X		
Concomitant medications 	X	X	X	X	X	X	X	X	X	X	X	X		X	X	X		X		
Adverse event assessment		X	X	X	X	X	X	X	X	X	X	X	X		X	X	X			

1. Record UPCR and urine protein assessments up to 1 year prior to screening (if available) in the medical history if patients were treated with Rituximab, other CD20+ monoclonal antibodies or calcineurin inhibitors, or other immunotherapy. Plasmapheresis within 12 weeks of screening should be captured in medical history.
2. The decision to modify the dose (i.e.: either to maintain, reduce or increase) will be made 2 weeks after each subject escalates to the 15 mg bid dose. This time point could vary for each subject.
3. Only the Screening 12-lead ECG can be single. The remainder should be triplicate 12 lead ECGs
4. 24 hr UPCR is be required for each dose escalation, and to confirm response at current dose. Total volume should be recorded and a 2 ml aliquot samples should be collected for PK assessment. Sites need to contact the patient prior to the visit day as a reminder to start the 24 hr urine collection. In the rare event that a patient does not bring in a 24-hour sample, a 24 hour sample needs to be started on the visit day and returned to the site upon completed collection. Urine protein:creatinine ratio (UPCR) and urine:albumin ratio (UACR), assessed in a sample drawn from a 24 hour collection is required at baseline and Study Week 12 (see schedule). At other time points defined in the Time and Events table, 24 hour collection is preferred. However, at these visits, a midstream midstream void sample may be used for assessments if a 24hr urine sample is not available.
5. PD samples must be collected before administration of the morning dose. Include urine samples for MCP-1 and MCP-1/creatinine ratio
6. Whole blood for analysis of absolute count and percentages of T cells, B cells and Natural Killer Cells.

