### 2.3 Study Endpoints

#### 2.3.1 Primary Efficacy Endpoints

The primary efficacy endpoint is the median reduction from baseline of urine protein to creatinine ratio (UPCR) of at least 20 % i.e. >20% by Week 12.

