### 3.1.4 *Summary Statistics*

Categorical data will generally be summarized with counts and percentages of subjects. The denominator used for the percentage calculation will be clearly defined. Continuous data will generally be summarized with descriptive statistics including n (number of non-missing values), mean, median, standard deviation, standard error of the mean, minimum, and maximum.

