### 3.1.5 *Hypothesis Testing*

Since this is a small open-label study with one treatment group, formal hypothesis testing is not applicable.

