## 3.4 Efficacy Assessment

Efficacy data will be summarized by randomized treatment based on the ITT Population. The primary and secondary efficacy endpoints are different than what was specified in the protocol. Partial remission, complete remission and associated endpoints (proportion and time to achievement of) as well as time to rescue therapy will not be calculated. See Section 6, Changes From Protocol-Specified Analyses for further details.

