## 6 CHANGES FROM PROTOCOL-SPECIFIED STATISTICAL ANALYSES

There are several changes to the protocol-specified statistical analyses provided below:

- Due to the small sample size and abbreviated summary of data, no per-protocol analyses will be carried out.
- Primary endpoint analysis changed from assessing median reduction from Baseline to Week 12 of UPCR of at least 20%, to producing summary statistics for UPCR and eGFR.
- Secondary endpoint analyses have been removed. Instead this data will be listed, including:
  - Time-to-Event analysis for Partial Remission and/or Complete Remission
  - Proportion of subjects with Partial Remission or Complete Remission
  - Change from Baseline Serum Albumin over time
  - Change in UACR from Baseline over time
  - Time to investigator or physician initiation of rescue therapy including glucocorticoids, new immunosuppressive agents, or new major treatment modalities
  - Duration between achievement of remission and relapse or treatment failure
  - Changes over time in Health Quality Assessment (SF-36 v2 and EQ-5D-5L)

Rationale: Following study CL011\_140, a randomized, double-blind, placebo-controlled dose-ranging study to evaluate the safety and efficacy of CCX140-B in subjects with Focal Segmental Glomerulosclerosis (FSGS), its results did not support the development of CCX140 in FSGS. Therefore a decision was made to not continue enrollment in study CL012\_140, which also investigates CCX140 in patients with FSGS and nephrotic syndrome. In addition, the efficacy and safety summaries will be limited to specific parameters and an abbreviated CSR will be developed for this study.

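### Does the SAP need a named lead UPCR measure, an interval for its median, and one rule for remission and rescue?

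*SAP*

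**What the plan says.** **Stated endpoint.** The objective in SAP 2.1.1 is "assessed as a median reduction from baseline of urine protein to creatinine ratio (UPCR) of at least 20" per cent by Week 12, and SAP 2.3.1 repeats it: "The primary efficacy endpoint is the median reduction from baseline of urine protein to creatinine ratio (UPCR) of at least 20" per cent. Neither says which urine sample is meant.

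**Planned analysis.** SAP 3.4.1 reads: "The primary efficacy endpoint analysis will include the following parameters: UPCR (Morning void), UPCR (24 hour Urine), and eGFR". Each is summarised descriptively, as change and percent change from baseline to Week 12.

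**Declared change.** SAP 3.4 warns: "The primary and secondary efficacy endpoints are different than what was specified in the protocol". Section 6 adds: "Primary endpoint analysis changed from assessing median reduction from Baseline to Week 12 of UPCR of at least 20%, to producing summary statistics". Those statistics cover both UPCR and eGFR. The reason given is that study CL011_140 did not support developing the drug in FSGS, so enrolment was not continued and the report will be abbreviated.

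**Inference and statistics.** SAP 3.1.5: "Since this is a small open-label study with one treatment group, formal hypothesis testing is not applicable". SAP 3.1.4 lists the summaries as "n (number of non-missing values), mean, median, standard deviation, standard error of the mean, minimum, and maximum".

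**Urine samples.** SAP Table 1, footnote 4, says UPCR "assessed in a sample drawn from a 24 hour collection is required at baseline and Study Week 12 (see schedule"). Protocol 6.2 and 6.8 call that collection mandatory.

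**Remission and rescue.** SAP 3.4 says these endpoints are not to be derived and points to Section 6. Section 6 says the secondary analyses are dropped and the data listed instead, then names proportions, times to event and duration. SAP 3.4.2 itemises listings without them, and SAP 2.3.2 still carries them as endpoints.

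**The concern.** A reader of Section 2 expects one UPCR result. Section 3.4.1 delivers two, unranked, beside eGFR. If one median showed a reduction of more than 20% and the other less, the report could lean on the better one.

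The morning-void label adds doubt. The protocol's visit sections ask for a first morning void for UPCR at ten visits (6.5, 6.7, 6.9 to 6.11, 6.13, 6.14, 6.16, 6.17 and 6.20). Day 1 and Week 12, the two visits being compared, are not among them. There the first morning void goes into the 24-hour collection.

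The stated endpoint is a median, yet the only standard error is for the mean. The 90% and 95% confidence intervals that Protocol 8.2.2 planned for change in proteinuria are gone, and Section 6 does not name them. Finally, a proportion or a time to remission cannot be listed unless it is derived, which SAP 3.4 excludes. At stake would be an identifiable main result and listing rules that can be programmed.

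**Working it through.** The current documents give no alpha, power or SD, so there is no design figure to reproduce. The sample size is 6 + 7 = 13 at most. Enrolment was stopped and the actual number is not stated.

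**1. Which UPCR leads?** The 24-hour sample is required at baseline and Week 12 (Protocol synopsis, Efficacy Assessments; SAP Table 1, footnote 4). At other visits a midstream void may stand in when no 24-hour sample exists. Only the 24-hour measure is compulsory at both ends of the comparison.

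**2. Which sample is the morning void?** The schedules in both documents mark a midstream spot void on Day 1 and at Week 12, and SAP 3.6.2 says one is taken at every timepoint. SAP 3.1.3 fixes baseline as the last assessment before first dose, and SAP 3.1.2 assigns visits. So spot records exist at both ends and the selection rules are written. What remains is a label mismatch.

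**3. What would an interval for the median add?** The exact order-statistic interval from rank k to rank n+1−k has coverage 1 − 2·Σ(i<k) C(n,i)/2ⁿ.

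| n | ranks | calculation | coverage |
|---|---|---|---|
| 5 | 1–5 | 1 − 2/32 | 93.75% |
| 6 | 1–6 | 1 − 2/64 | 96.9% |
| 7 | 1–7 | 1 − 2/128 | 98.4% |
| 8 | 1–8 | 1 − 2/256 | 99.2% |
| 9 | 2–8 | 1 − 2(1+9)/512 | 96.1% |
| 13 | 3–11 | 1 − 2(1+13+78)/8192 | 97.8% |

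At n=8 the next narrower choice, ranks 2–7, gives 1 − 2(1+8)/256 = 93.0%. So from 6 to 8 subjects the interval is the printed minimum and maximum. At 5 or fewer no 95% interval of this kind exists. A gain starts at n=9. At n=13, with an assumed log-ratio SD of 0.5 and a true 20% reduction, the typical interval is about −48% to +22%, against a range of about −65% to +80%.

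**4. How often would the two medians straddle 20%?** Assumptions, none from the documents: lognormal ratios, SD of the log ratio 0.3 to 0.7, correlation 0.5 to 0.95, and the same true change in both measures. Simulated shares of trials:

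| True reduction | n=6 | n=13 |
|---|---|---|
| 0% | 4–27% | 2–24% |
| 10% | 9–33% | 9–34% |
| 20% | 14–37% | 19–39% |
| 30% | 9–34% | 8–32% |
| 40% | 2–25% | 0.3–17% |

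At n=13 the peak lies at 20% because the truth then sits on the threshold. Both medians are printed whether or not one is called the lead, so these shares do not change when one is named.

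**5. Can SAP 3.4, 3.4.2 and Section 6 be followed together?** Yes, if Section 6 means that the analyses are removed and the underlying data listed. SAP 3.4.2 introduces its items as examples, so an omission there is not a contradiction. The ingredients are covered: albumin and creatinine in 3.4.2, medications in 3.3.6, procedures in 3.3.7, and all available data in Section 7.

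**The case for a change.** The strongest reply is that printing everything is itself the problem: with two unranked medians, the choice of headline comes after the data are seen. There is a number for this. At n=6, SD 0.5, correlation 0.7 and a true 10% reduction, at least one median shows 20% or more in 42% of simulated trials, against 29% for a single pre-named measure. That would matter if a success claim rode on it. None does: Section 6 withdraws the 20% assessment, and anyone favouring one version does so with the other in the same table.

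Protocol 8 also says that changes to principal features go into a protocol amendment, and the SAP still rests on Amendment 1.0. Whether this change qualifies is for the sponsor to judge. It is disclosed with its reason, and Protocol 8 places the SAP in the study report.

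On the lost confidence intervals, Protocol 8.2.1 never planned one for the primary endpoint. Those in 8.2.2 belong to the secondary analyses, which Section 6 removes as a group.

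What stands is editorial: leftover 20% wording in Section 2, no explicit lead in 3.4.1, loosely worded bullets in Section 6, and two names for the spot sample.

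**Conclusion.** No change to the plan is called for. The points are slips of wording and gaps that an analyst fills sensibly: 24-hour UPCR first, the scheduled spot void as the other UPCR parameter, and no derivation of remission or rescue. No planned estimate or conclusion would move. The order-statistic interval is only a coverage label at n=6 to 8, is unavailable at the 95% level with 5 or fewer subjects, and narrows the picture only from n=9, a number that may not have been reached. If it was, the listings let a reader form the interval.

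This rests on three readings: that Section 6 governs over the carried-over text in Section 2, that listed data means source data, and that the report makes no claim against 20%. The coverages are exact; the straddling shares depend on assumed SDs and correlations and on a benchmark the SAP has dropped.

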## Methodology

This is an open label clinical trial to test the efficacy, safety, pharmacokinetics and tolerability of ascending doses of CCX140-B in subjects with primary FSGS and nephrotic syndrome. Throughout the treatment period, any changes in background medications should be limited to settings in which the Investigator deems it to be necessary for the safety of the subject.

Eligibility requirements are detailed in the inclusion and exclusion criteria.

The screening period will be up to 28 days.

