#### **4.3. Exclusion Criteria**

1. Pregnant or nursing
2. History of organ transplantation, including renal transplantation

3. Currently on an organ transplant waiting list or there's a reasonable possibility of getting an organ transplant within 6 months of screening
4. Histological FSGS subtype of collapsing variant
5. Subjects who initiated, discontinued or changed dose of rituximab or other anti-CD20 monoclonal antibodies **within 16 weeks (4 months)** prior to screening are excluded. Subjects who initiated treatment with rituximab or other anti-CD20 monoclonal antibodies **>16 weeks (4 months)** prior to screening are permitted if deemed safe by the investigator and only if they are intended to remain on continued, unchanged therapy at a dosing interval that has been documented to achieve continuous B cell depletion for the given patient. UPCR and other urine protein assessments up to 1 year prior to screening (if available) that were performed in these patients as part of the clinical routine should be recorded in the medical history.
6. Subjects who discontinued Rituximab or other anti-CD20 monoclonal antibodies **>16 weeks (4 months)** prior to screening *without* confirmed recovery of CD20+ B cell population to within normal range are excluded. Subjects who discontinued rituximab or other anti-CD20 monoclonal antibodies **>16 weeks (4 months)** prior to screening *with* confirmed recovery of CD20+ B cell population to within normal range are permitted in the study. UPCR and other urine protein assessments up to 1 year prior to screening (if available) that were performed in these patients as part of the clinical routine should be recorded in the medical history.
7. Subjects who initiated or increased the dose of calcineurin inhibitors, or other immunotherapy, within 12 weeks prior to screening are excluded; dose reductions to maintain calcineurin inhibitors at optimal safe levels are permitted. Subjects who initiated a treatment with calcineurin inhibitors, or other immunotherapy **>12 weeks** are permitted. UPCR and other urine protein assessments up to 1 year prior to screening (if available) that were performed in these patients as part of the clinical routine should be recorded in the medical history.
8. Subjects taking glucocorticoids at dose greater than 10 mg/day prednisone equivalent within 4 weeks prior to screening are excluded.
9. Plasmapheresis within 12 weeks prior to screening
10. Body Mass Index (BMI)  $\geq 40$

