## 7.7. Concomitant Medications and Restrictions

The doses of RAAS inhibitors must be stable prior to Day 1, and remain stable throughout the course of the study, unless adjustment is required for the safety of the subject. For eligible subjects willing to participate in the Open-Label Extension (after Week 12), the doses of RAAS inhibitors and other concomitant drugs may be modified per physician judgment. Subjects who require addition of a new immunosuppressive or immunomodulatory agent may continue treatment with CCX140-B if they have not met criteria for treatment failure, the case has been discussed with the study director and there is agreement to continue treatment. Plasmapheresis is not allowed at any point during the course of the study.

CCX140-B is primarily cleared through CYP3A4 metabolism. Subjects taking strong CYP3A4 inducers (e.g., phenytoin, rifampicin, carbamazepine, St. John's Wort) will be excluded from this clinical trial since these drugs may substantially reduce the CCX140-B plasma levels. In addition, subjects taking strong CYP3A4 inhibitors (e.g., boceprevir, clarithromycin, conivaptan, grapefruit juice, indinavir, itraconazole, ketoconazole, lopinavir/ritonavir, mibefradil, nefazodone, nelfinavir, posaconazole, ritonavir, saquinavir, telaprevir, telithromycin, and voriconazole) will be excluded as these drugs may substantially increase the CCX140-B plasma levels.

All concomitant medications taken during the course and up to 12 weeks prior to screening Day 1 study should be recorded meticulously on the concomitant medication pages of the CRF.

Prior treatment with rituximab or other anti-CD20 monoclonal antibodies and corresponding levels of CD20+ B cells need to be recorded up to 1 year prior to screening.

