### 7.7.1. Rescue Therapy

If the investigator decides that a subject needs to receive rescue therapy the subject will be considered a treatment failure. Rescue therapy is considered any new therapy or required dose increase of an existing concomitant therapy (other than allowed per [Section 7.7. Concomitant](#)

Medications and Restrictions) that is required for the safety of the patient and to treat the underlying disease of FSGS.

This would include but is not limited to the initiation of high dose glucocorticoid therapy, new immunosuppressive agents such as calcineurin inhibitors, cyclophosphamide, MMF, monoclonal antibodies, or other major treatments (e.g. plasmapheresis, dialysis).

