## 3.2 Analysis Populations

### 3.2.1 *Intent-to-Treat (ITT) Population*

The ITT Population is defined as all subjects who have received a dose of the study drug and have at least one post-baseline efficacy assessment.

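### UPCR and eGFR summaries can include values taken after permitted changes to other therapy, mainly at extension visits, and no table separates them

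*SAP*

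**What the plan says.** SAP 3.4 bases efficacy on the ITT population, which SAP 3.2.1 defines as "all subjects who have received a dose of the study drug and have at least one post-baseline efficacy assessment". SAP 3.4.1 keeps three parameters: morning-void UPCR, 24-hour UPCR and eGFR. It states "This will be summarized by treatment group over time using descriptive statistics" and adds "Both change from baseline to Week 12, and percent change from baseline to Week 12 will be included in the summary". SAP 3.1.4 counts non-missing values. None of these sections excludes, flags or splits a value because another drug was started or increased.

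Protocol 7.7 permits such changes in two ways. A subject who has not met the treatment-failure criteria may receive a new immunosuppressive or immunomodulatory agent and remain on CCX140-B, after discussion and agreement with the study director. In the extension, "the doses of RAAS inhibitors and other concomitant drugs may be modified per physician judgment". Section 7.7.1 has a matching exemption: "Rescue therapy is considered any new therapy or required dose increase of an existing concomitant therapy (other than allowed per" Section 7.7). Before Week 12 the rule is tighter. The Synopsis (Methodology) says "any changes in background medications should be limited to settings in which the Investigator deems it to be necessary" for the subject's safety.

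Subjects can bring background therapy with them. Exclusion 7 of Protocol 4.3 admits some of them: "Subjects who initiated a treatment with calcineurin inhibitors, or other immunotherapy" more than 12 weeks earlier are permitted. Exclusion 8 reads "Subjects taking glucocorticoids at dose greater than 10 mg/day prednisone equivalent within 4 weeks prior to screening are excluded", so lower doses are allowed.

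**The concern.** The trial has one arm, so change from baseline is the only efficacy evidence, and SAP Section 6 reduces that evidence to the UPCR and eGFR summaries. If a subject's calcineurin inhibitor, glucocorticoid or RAAS inhibitor is raised in the extension and proteinuria then falls, the table shows the fall as change on CCX140-B. Protocol 1.5 itself describes RAAS blockers as treatment for proteinuria.

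The protocol endpoints that took rescue into account are gone. Both remission definitions required that the subject not be a treatment failure, and time to rescue was an endpoint. SAP 3.4 calculates neither. What is at stake is how a reader interprets the descriptive tables in the abbreviated study report.

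**Working it through.** The current plan states no power, error rate or effect-based sample size for this point, so there is no such figure to reproduce. The check is of the rules, followed by simple arithmetic on assumed inputs.

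**1. Which values enter.** ITT membership (SAP 3.2.1) needs a dose and one post-baseline efficacy value. The statistics (SAP 3.1.4) use non-missing values. Scheduled visits keep their recorded label. Unscheduled and early-termination values are placed by date when no scheduled value exists (SAP 3.1.2). Drug changes play no part, so by default all observed values are summarised.

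**2. Visit windows.** The midpoint rule in SAP 3.1.2 reproduces the plan's eGFR window for Week 12: (57 + 85)/2 = 71 and (85 + 113)/2 = 99, hence Days 72 to 99. For 24-hour UPCR, the next routine collection after Week 12 in Protocol Section 6 is Week 28 (Day 197). The upper limit becomes (85 + 197)/2 = 141. A later unscheduled or early-termination value could therefore stand in for Week 12, but only if the mandatory Week 12 collection is missing.

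**3. Where exposure lies.**
- *Through Week 12:* narrow. Rescue makes the subject a treatment failure (Protocol 7.7.1), and treatment failure ends dosing (Protocol 5.2.1). Exclusion 24 bars other systemic disorders expected to need systemic corticosteroids or immune modulators. Continuing anti-CD20 therapy must stay unchanged unless safety prevents it (Protocol 7.7). What remains is a safety-driven change not made to treat FSGS, a new agent under the 7.7 continuation clause, or a stand-in value as in step 2.
- *After Week 12:* wider. Doses of RAAS inhibitors and other concomitant drugs may be changed at the physician's discretion, and Section 7.7.1 does not count what Section 7.7 allows as rescue. Such a subject can stay on CCX140-B and keep contributing values. The example windows run to Week 52.

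**4. What would separate the values.** No table does. SAP 3.3.6 lists medications by subject, SAP Section 6 says rescue data will be listed, and SAP Section 7 lists all available data. SAP 3.3.1 tabulates reasons for discontinuation, but a permitted change need not lead to discontinuation.

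**5. Size for one affected subject.** Let d be the fall in UPCR, in points of that subject's baseline, due to the other drug. With n subjects at the visit, mean percent change moves by d/n towards benefit. The planned sizes are n = 13 (both stages) and n = 6 (first stage); d is assumed.

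| d | n = 13 | n = 6 |
|---|---|---|
| 0 | 0 | 0 |
| 25 | 25/13 = 1.9 | 25/6 = 4.2 |
| 90 | 90/13 = 6.9 | 90/6 = 15.0 |

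The number of subjects at extension visits is not given. Because the divisor is n, the same d moves the mean more when fewer subjects contribute.

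**6. Leaving the subject out is not neutral.** Let m be the others' mean percent change and m + g the subject's value had the drug not been given, with g > 0 meaning worse. Without the drug, the full mean would be m + g/n. The restricted mean is m, which is g/n more favourable. For an assumed g of 0 to 50 this is 0 to 50/13 = 3.8 points, or 0 to 50/6 = 8.3 points. The all-observed mean is m + (g − d)/n. If g = d the two summaries agree although both favour the drug, so the count of flagged subjects has to be reported too.

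**The case against.** The strongest reply is that summarising everything observed is a legitimate treatment-policy choice. With at most 13 subjects, anyone can trace a drug change through the listings. No hypothesis is tested (SAP 3.1.5), enrolment was not continued, and no decision is shown to depend on these tables. All of that stands, and it limits the point to a cheap improvement. It does not remove it, because the tables themselves give no sign that other therapy changed.

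The sizes are also open to challenge. They concern the mean, with assumed d and g. The SAP also reports the median, minimum and maximum, and one subject need not move a median by d/n. That is correct, and the figures are illustrations only.

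The change from baseline that SAP 3.4.1 names is to Week 12. Summaries at extension visits are read from the words on time course and from an example window table for eGFR. If the final tables stop at Week 12, only the narrow routes in step 3 remain. The SAP 3.4.1 text also breaks off mid-sentence, and the programming specifications are in a separate document, so a flag could exist there unseen.

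A reader might infer more than the documents support:
- *That the Week 12 result is contaminated by rescue.* Rescue ends dosing, and a post-rescue value reaches Week 12 only as a stand-in for a missing scheduled one. It may also be too close to the start of rescue to differ much.
- *That dropping the per-protocol and deviation analyses removed the safeguard.* A permitted drug change is not a deviation, so those analyses would not have isolated it.
- *That Section 7.7.1 must be rewritten.* Section 7.7 is best read as deciding treatment failure first, and a protocol change would add little now that enrolment has stopped.

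**Conclusion.** The point holds in a limited form. The only efficacy summaries left carry no rule for values taken after permitted changes to other therapy. In a single-arm trial, any resulting fall would be shown as change on CCX140-B. Exposure is mainly at extension visits and only rarely at Week 12. The effect is conditional and descriptive: the documents report no affected subject. For one such subject the mean would move by 0 to 6.9 points at n = 13 or 0 to 15.0 at n = 6, for d assumed between 0 and 90.

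The conclusion rests on two readings: that a summary without an exclusion rule uses all non-missing values, and that the time-course summary extends past Week 12.

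**What to change.** Make the change in the SAP before database lock. If lock has passed, document it as a deviation in the study report, as SAP Section 1 provides.

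1. Flag UPCR and eGFR values taken after the start of a new immunosuppressant or glucocorticoid. Also flag values after a recorded dose increase of either, or of a RAAS inhibitor, where the CRF captures it.
2. Show the UPCR and eGFR summaries with all observed values, and again without flagged values.
3. State how many subjects and values are flagged.
4. Footnote that the restricted summary omits subjects who needed added therapy and may favour the drug.
5. If no subject is affected, say so in one line and omit the second table.

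The cost is one flag and one small repeat table. SAP Appendix A already puts medication start dates, with imputation of partial dates, into the ADaM data. There are two limits: the restricted table has fewer values, and the documents do not show whether the CRF records dose increases, so some permitted changes may go unflagged.
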